Potential benefits for participants of the randomized trial exist for both groups of children (SB-TEAM and eUC). The goal is for children in the SB-TEAM group to have improved symptom assessment, adherence

to preventive medications, and appropriate tailoring of therapy, thus they may experience less morbidity from asthma. Although children in the eUC group will not be receiving medication through school or telemedicine asthma visits, we will prompt their PCP to provide guideline based asthma care including prescription of the appropriate preventive medications and will provide regular reminders to PCPs and caregivers to care for the child's asthma. Improved asthma management should result in reduced morbidity for these children. Since the medications used in this study are safe and effective at the doses administered, and are strongly recommended by the national asthma guidelines, we anticipate that the intervention benefits will outweigh the minimal risk of participation.

11. Analysis

Sample Size:

This study is designed to have adequate power to detect the smallest clinically significant difference in mean SFDs post-intervention between the intervention and enhanced usual care groups. Based on our previous data, we estimate the pooled standard deviation of SFD at 2.8 and within-subject correlation at 0.3. Power was calculated for the intervention effect on SFD with at least two assessments for each subject. We anticipate <15% attrition, as attrition was minimal (<10%) in the prior study, and therefore plan to enroll 400 children. With a final sample of 336, we will have 90% power to detect a difference of 0.8 symptom-free days or greater per 2-wk. period. This difference is supported by our prior data, and would justify continuing the intervention. There are more than 11,000 students in pre-k through 4th grade in the RCSD and at least 6,600 entering kindergarteners in a 3 year period. Conservatively assuming an asthma prevalence of 9%, more than 1,584 students have asthma, and approximately ½ of these students (792) have persistent asthma. In our prior study, we enrolled 74% of eligible subjects. A conservative estimate would allow us to enroll 120 subjects/year (60%), which is more than adequate to meet our sample size.

Primary Analysis:

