Cost Effectiveness Analysis: *Establish the cost-effectiveness of the intervention with a specific focus on ultimate sustainability and dissemination.* We will assess health and economic benefits of SB-TEAM from both the societal and the Medicaid perspective. We also will use *Diffusion of Innovations Theory* to help understand how this innovative model can be maintained in the current system of care through city schools.

We will assess health and economic benefits of SB-TEAM compared to enhanced usual care by using cost-effectiveness (CE) methodology. The time horizon of the study will be one school year (September-June). Four cohorts that will complete the study in consecutive years will be analyzed as one stacked study cohort. The basecase analysis will be conducted from the societal perspective which includes all identifiable costs and benefits, regardless of whom they impact. The majority of children in the study

are eligible for Medicaid (73% based on the prior study), thus a second analysis will take the Medicaid perspective. The benefits of the intervention will be measured as the number of symptom-free days during the school year.

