We will consider the total costs of initiating and maintaining the program as well as the incremental cost-effectiveness ratio (ICER) of the SB-TEAM vs. eUC, which is the ratio of differences in costs between the 2 study groups to the difference in the number of symptom-free days (SFD) gained between the 2 groups. The main outcome for the analysis from the societal perspective will be an incremental cost-effectiveness ratio (ICER), which is the ratio of net program costs to the number of symptom-free days (SFD) gained, $ICER = (\Delta Medical + \Delta Productivity + \$Program) / \Delta SFD$, where $\Delta = (SB-TEAM) - (eUC)$. We will bootstrap the ICER to estimate standard error and to evaluate the uncertainty around the point estimate. The ICER will be compared to similar estimates from the literature. An acceptability curve, linking various values of 1 SFD to the probability of SB-TEAM being cost-effective, will be plotted. The study from the Medicaid perspective will use the cost-benefit approach to economic evaluation. Benefits will be described as the net difference in medical and productivity costs between children in the SB-TEAM and eUC groups. The cost is equivalent to the cost of the program. Equation: *Net Monetary Benefit* = $\Delta Medical - \$Program$.

Process Evaluation: Descriptive statistics will be used for the process evaluation, looking in particular at the efficiency of the program implementation along with the responses from parents, primary care providers, and school nurses and administrators about convenience, scheduling, satisfaction, and sustainability.

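### The only numerical uncertainty measure named for the ICER is a bootstrap standard error, which does not settle on the plan's own inputs and is often inflated

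*Combined protocol and SAP*

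**What the plan says.** Section 11 (Analysis), Cost Effectiveness Analysis, takes the societal perspective as its base case and makes the ICER its main outcome. The ICER is defined there as a quantity "which is the ratio of net program costs to the number of symptom-free days (SFD) gained", so its denominator is the between-group SFD difference. The effect is counted over the school year: "The benefits of the intervention will be measured as the number of symptom-free days during the school year".

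On uncertainty the section says two things. First: "We will bootstrap the ICER to estimate standard error and to evaluate the uncertainty around the point estimate". Second: "An acceptability curve, linking various values of 1 SFD to the probability of SB-TEAM being cost-effective, will be plotted". It names no type of confidence interval, no number of replicates, no cost-effectiveness plane, and no rule for replicates in which the SFD difference is zero or negative.

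The inputs that fix the precision of the denominator are under Sample Size in the same section. The variability is given as follows: "we estimate the pooled standard deviation of SFD at 2.8 and within-subject correlation at 0.3". The calculation takes two or more assessments per child, and its result is: "With a final sample of 336, we will have 90% power to detect a difference of 0.8 symptom-free days or greater per 2-wk. period".

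**The concern.** A ratio estimate has a usable standard error only if its denominator stays well away from zero. When the sampling distribution of the denominator reaches zero, the variance of the ratio is not finite. A few replicates with a tiny SFD difference then decide the bootstrap standard deviation. Adding replicates does not help, because it brings in more such extremes. A symmetric bar built on that figure would also misdescribe a skewed distribution.

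Study objective 6 is to establish cost-effectiveness with a view to sustainability and dissemination, and the plan compares the ICER with published estimates. If the figure beside the ICER depends on the seed and the number of replicates, that comparison loses its meaning, and a clear economic result may read as uninformative.

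**Working it through.** **1. Reproduce the plan's power.** Inputs from Sample Size: SD 2.8, within-subject correlation 0.3, 336 children (168 per arm), difference 0.8 SFD per two weeks. Two-sided alpha of 0.05 is from Primary Analysis. The SD of the mean of m assessments is 2.8 × √[(1 + (m − 1) × 0.3)/m].

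- m = 2: 2.8 × √0.65 = 2.257.
- SE of the difference: 2.257 × √(2/168) = 0.246.
- Effect/SE: 0.8/0.246 = 3.25. Power = Φ(3.25 − 1.96) = 90%, as stated.

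**2. Distance of the denominator from zero.** Converting to SFD per school year multiplies effect and SE alike, so effect/SE does not change. Three assessments are the post-intervention follow-ups named in Primary Analysis. Four is the schedule of calls every other month plus the final visit.

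| Assessments | SE | 0.8/SE | Replicates with SFD difference ≤ 0 (observed effect 0.8) | Chance of at least one in 1,000 |
|---|---|---|---|---|
| 2 | 0.246 | 3.25 | 0.058% | 44% |
| 3 | 0.223 | 3.59 | 0.017% | 15% |
| 4 | 0.211 | 3.80 | 0.007% | 7% |

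**3. First-order standard error.** Costs are not in the documents. Illustrative assumptions: cost difference $200, SD $1,500 per child, 17 two-week periods, no cost-effect correlation.

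- SE of cost difference: 1,500 × √(2/168) = $164, a coefficient of variation (CV) of 0.82.
- ICER: 200/(0.8 × 17) = $14.7 per SFD.
- First-order SE, two assessments: 14.7 × √(0.82² + (1/3.25)²) ≈ $13. Three and four assessments also give about $13.

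**4. Simulated bootstrap, true effect 0.8, 2,000 replicates per trial** (normal approximation to the bootstrap, observed effect varying between trials):

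| Assessments | Median SE | 95th percentile | Trials above twice first-order |
|---|---|---|---|
| 2 | about $28 | about $2,000 | about 51% |
| 3 | about $20 | about $1,100 | about 42% |
| 4 | about $17 | about $800 | about 37% |

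The 5th percentile with two assessments is about $9. Repeat runs moved the medians by a dollar or two, the shares by a few percentage points, and the 95th percentiles by more.

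**5. Same data, new random numbers** (observed effect exactly 0.8, two assessments). The median SE rises from about $21 with 1,000 replicates to about $45 with 10,000. The 97.5th percentile of the same replicates stays near $55 and tightens, from $51–$61 to $54–$57 (5th–95th percentile across seeds).

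**6. Dependence on the cost assumption.** Scale the ICER to 1 and take a cost-difference CV of 0.25, with the observed effect at 0.8.

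| Assessments | First-order SE | Median SE, 1,000 replicates | Median SE, 10,000 replicates |
|---|---|---|---|
| 2 | 0.40 | 0.95 | 2.55 |
| 3 | 0.37 | 0.60 | 1.00 |
| 4 | 0.36 | 0.52 | 0.66 |

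With two assessments and 1,000 replicates, a CV from 0 to 0.5 gives medians of 0.92 to 1.09, and a cost-effect correlation from −0.5 to 0.5 gives 1.30 to 0.60. For two assessments and CV 0.25, the percentile interval is 0.44 to 2.67 (1,000 replicates) and Fieller gives 0.44 to 2.70.

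**7. Smaller true effect.** The expected share of replicates with a non-positive SFD difference, averaged over trials, is Φ(−(effect/SE)/√2). At 0.4 days this is 12.5%, 10.2% and 9.0% for two, three and four assessments.

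**The case against.** The plan does not rest on the standard error alone. The sentence that names it also speaks of evaluating uncertainty in general, and the acceptability curve comes from joint cost and effect replicates without using the ratio's standard error. No symmetric interval, test or decision rule is tied to the standard error. All of this stands, and a reader who inferred that the plan offers no sound uncertainty output would be wrong.

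Two assessments is the least favourable setting. With three or four, the typical standard error is much closer to first-order. That stands too, but the upper tail does not go away: about 37% of trials still exceed twice the first-order value with four.

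A reader might also infer that an uncertain result could be made to look clear. The calculations do not support that. The error is almost entirely inflation, and the estimate ± 1.96 bootstrap SE covered the true ICER in 98–99% of simulated trials.

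Nor is it a material problem at the planned effect that negative ratios mix savings with benefit and extra cost with harm. The median trial has 0.05% or fewer replicates with a non-positive SFD difference. This matters only if the effect is well below plan.

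Finally, net benefit over a range of values carries much the same information as the planned curve. That is so, but the curve does not put a dependable numerical interval beside the main result.

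**Conclusion.** The point holds in a limited form. The one numerical measure of uncertainty named for the main economic outcome does not converge on the plan's own SFD inputs, even at the planned effect. It depends on the seed, rises with the number of replicates, and is often well above the first-order value. The likely consequence is that a clear result looks uninformative. To call every such standard error unusable would go too far, since many trials would yield a moderate one.

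The distance from zero (3.25, about 3.6 and 3.8 standard errors) follows from the documents. The dollar figures rest on one assumed pair of costs, 17 periods, zero correlation and a normal approximation, and are illustrative. The instability itself persists over the CVs and correlations tried. The matter is confined to the economic analysis; the primary SFD test is not affected. It should be corrected because the repair is cheap.

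**What to change.** Do not report the bootstrap standard error as the uncertainty of the ICER. From the same joint cost and effect replicates:

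- Report incremental net benefit (value per SFD × SFD difference − cost difference) with a 95% confidence interval over a stated range of values per SFD. The plan already uses a net-benefit form for the Medicaid perspective.
- Give a Fieller or percentile interval for the ICER when the SFD difference is clearly separated from zero, with that criterion set in advance. Otherwise rely on net benefit and the cost-effectiveness plane. The condition is needed: at a true effect of 0.8, about 10%, 5% and 3% of trials (two, three and four assessments) would not show a significant SFD difference, and percentile limits of the ratio then fail as well.
- State the number of replicates and keep the acceptability curve.

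The cost is a change of wording in the analysis plan and a little extra analysis. No new data are needed and the sample size does not change.

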Three main categories of costs to be considered include programmatic costs, productivity costs, and medical costs estimated at the individual child level. Programmatic costs include costs of initiating and running the program, hiring and training staff, purchasing or leasing equipment, staff travel, and information system costs. Costs associated with this study that would not exist as part of the intervention will not be included, as we do not anticipate that they would continue beyond the duration of the study. Per person programmatic costs will be calculated by dividing the total costs of the program by the total number of children with persistent asthma in the schools. We will determine *productivity/opportunity costs* based on the amount of time parents take from work to care for sick children or take them to a doctor. Time from work will be valued at the median of the pay scale estimates based on age, race and gender specific wages from the Bureau of Labor Statistics. We will assess the impact of the intervention on *medical* costs using parent-reported health services use data and medical record review. We will ask parents at each follow-up about their child's ER or physician visits, hospitalizations, medical procedures, use of medications and durable equipment. Healthcare use will be converted to costs using the NYS Medicaid fee schedule and other sources. Annual medical costs per person will be analyzed using a 2-part model to adjust for zero expenses in a given year. All costs will be adjusted to the last year of the intervention using the appropriate component of the Consumer Price Index (CPI).

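### The Medicaid net monetary benefit formula has the wrong sign under the plan's own definition of delta, so medical savings from SB-TEAM count as losses

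*Combined protocol and SAP*

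**What the plan says.** All of this stands in the combined protocol and SAP, section 11 (Analysis), under Cost Effectiveness Analysis.

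- **Definition of delta.** It appears once, attached to the ICER: "where $\Delta = (SB-TEAM) - (eUC", that is, SB-TEAM minus eUC.
- **Societal result.** "ICER = (\Delta Medical + \Delta Productivity + \$Program) / \Delta SFD". The medical difference is added to the program cost to give net cost.
- **What the medical term measures.** "Healthcare use will be converted to costs using the NYS Medicaid fee schedule and other sources". It is an amount of money spent, so a higher value is worse.
- **Medicaid result, in words.** "Benefits will be described as the net difference in medical and productivity costs between children in the SB-TEAM and eUC groups". The other side of the balance follows: "The cost is equivalent to the cost of the program". No direction is given for the difference.
- **Medicaid result, as an equation.** "Net Monetary Benefit* = $\Delta Medical - \$Program". Delta is reused here and not redefined.

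**The concern.** A net benefit should rise when the program averts spending. Under the stated delta, averted spending is a negative number, and this equation carries it into the benefit with its sign unchanged. The same quantity is treated as a cost in the ICER and as a benefit in the Medicaid line of the same paragraph.

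The Medicaid view is the second of two stated perspectives. The plan justifies it by the share of children eligible for Medicaid (73% in the prior study), and it serves objective 6, on cost-effectiveness and sustainability. This equation is the only formula given for it. An analyst who codes delta once, as defined, and uses it in both formulas would report a payer result that moves in the wrong direction.

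The wording and the equation also disagree on content: the sentence counts productivity costs in the benefit and the equation does not.

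**Working it through.** The plan states no cost, ICER or net benefit figure, so there is nothing to reproduce. The check is algebra, followed by an illustration with assumed amounts.

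**Inputs from the plan.** Let M be medical cost per child, P the program cost per child, and dM = M(SB-TEAM) - M(eUC), the plan's delta.

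**Equation as written.**

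NMB(written) = dM - P = M(SB-TEAM) - M(eUC) - P

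**Benefit minus cost, with benefit taken as medical cost averted.**

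NMB(correct) = [M(eUC) - M(SB-TEAM)] - P = -dM - P

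**Difference.**

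(dM - P) - (-dM - P) = 2 x dM

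The two agree only when dM = 0.

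**Cross-check against the ICER.** With productivity left out, the ICER numerator is dM + P, the net cost. Net benefit should be its negative, -(dM + P) = -dM - P. This matches the corrected form and not the written one.

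**When the result is positive.** As written, NMB > 0 requires dM > P: SB-TEAM must raise medical costs by more than the program costs. In the corrected form, NMB > 0 requires -dM > P: it must save more than the program costs. When the medical difference in either direction is smaller than P, both forms are negative and only the size is wrong. When it is larger than P, the sign of the conclusion reverses.

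**Illustration.** Assumed values in USD per child: P = 300 and M(eUC) = 1,000.

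| M(SB-TEAM) | dM | ICER numerator without productivity | NMB as written | NMB corrected | Written minus corrected |
|---|---|---|---|---|---|
| 200 | -800 | -500 | -1,100 | +500 | -1,600 |
| 600 | -400 | -100 | -700 | +100 | -800 |
| 1,000 | 0 | +300 | -300 | -300 | 0 |
| 1,400 | +400 | +700 | +100 | -700 | +800 |

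In every row the corrected value is minus the ICER numerator, and the last column is 2 x dM. The written formula ranks the four scenarios in exactly the reverse of their true order.

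**Productivity.** If the sentence were followed instead and productivity entered the benefit, the corrected result would be -dM - dProductivity - P. That is minus the full societal numerator, so the Medicaid analysis would contain the same cost components as the societal one.

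**The case against.** The best defence is that this is a slip of notation. Delta is defined in a clause attached to the ICER. Several sentences later the text turns to a cost-benefit approach and describes a benefit, with the program as its cost. Benefit minus program cost is coherent if the medical term means savings, eUC minus SB-TEAM, and that may well be what was intended. A careful economist would probably notice, and the inputs are collected either way, so the sign could be put right at any time before reporting.

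It is also fair to say that the Medicaid analysis is secondary. The societal perspective is the base case, and cost-effectiveness is the last of six objectives. Nothing in randomization, data collection, sample size, the primary analysis or the ICER depends on this line. The size of the error in practice is unknown, because the plan gives no costs.

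On productivity, the text alone does not say whether the sentence or the equation is the intended one.

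The limits on scope and on known size stand, and the harm does depend on the formula being applied literally. The savings reading does not rescue the text. It contradicts the only definition of delta, the verbal description gives no direction, and the ICER needs the opposite direction from the same symbol. The equation is legible and complete as it stands, and nothing in the text points to a lost sign.

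**Conclusion.** The concern holds. Under the plan's only definition of delta, the Medicaid net monetary benefit is wrong by 2 x delta-Medical. For any positive program cost, a program that saves medical money can never show a positive net benefit as the formula is written, and larger savings look worse. A positive result needs an increase in medical cost greater than the program cost.

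This rests on two things that the plan states (delta is SB-TEAM minus eUC; the medical term is a cost) and on the ordinary meaning of net benefit. It does not rest on the illustrative dollar amounts. The error is confined to the Medicaid-perspective analysis, but there it governs the direction of the result, so the equation must be corrected before it is used. The mismatch over productivity is a separate, smaller inconsistency, and the sign correction stands without it.

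**What to change.** Keep delta as defined and replace the Medicaid equation with:

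Net Monetary Benefit = (Medical eUC - Medical SB-TEAM) - Program, equivalently -(delta-Medical) - Program.

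Writing out the group order removes any dependence on the sign convention.

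Then make the introductory sentence agree with the equation. Removing productivity costs from the Medicaid benefit is the simpler choice. The plan defines them as parents' time away from work, which is not a Medicaid expense, and they are already counted in the societal ICER. If the investigators do want them in the Medicaid analysis, the equation needs a matching term, (Productivity eUC - Productivity SB-TEAM), and a stated reason.

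The cost is one equation and one sentence. No data, sample size or study procedure changes.
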